8.1.1 Analysis Population

The following populations will be used for analyses in this study:

Full Analysis Set (FAS) population includes all subjects who complied with GCP and received at least one dose of study drug and had at least one post-treatment efficacy

assessment. FAS is the primary population for the efficacy analysis. In general, efficacy analysis will be performed for all subjects regardless dose escalation.

The Safety set consists of all subjects who received at least one injection of study drug.

Pharmacokinetic assessments will be conducted on all subjects who were administered at least one dose of study drug and have at least one post-dose sample collected for the determination of serum adalimumab concentration.

8.1.2 Planned Methods of Statistical Analysis

Descriptive statistics will be provided. These include the number of observations, mean, standard deviation, minimum, median, and maximum for continuous variables; and counts and percentages for discrete variables. The analysis will be performed using SAS® (SAS Institute Inc., Cary, NC, USA).

8.1.3 Demographics and Baseline Characteristics

Demographics and Baseline characteristics of the study subjects will be summarized using descriptive statistics.

8.1.4 Statistical Analyses of Efficacy

8.1.4.1 Primary Efficacy Variable

The primary efficacy endpoint is the proportion of subjects achieving Clinical Response (remission and improvement) at Week 16.

Clinical Response is defined as reduction of 1 (if the subject's Baseline skin score is 3) or 2 (if the subject's Baseline skin score is 4 or higher) relative to Baseline, according to JDA severity index of GPP in GPP Medical Care Guideline 2014 in Japan ([Appendix I](#)).

8.1.4.2 Secondary Efficacy Variables

Discrete variables will be summarized by counts and percentages, and continuous variables will be summarized by descriptive statistics on the items below at each visit.

The subjects who have missing data for any reason such as early terminated subjects will be included into analysis using NRI for discrete variables or LOCF for continuous variables.

For secondary efficacy variables, see Section [5.3.3.2](#).

8.1.6 Other Statistical Analyses of Efficacy

The subgroup analysis listed below is planned. Proportion of subjects achieving Clinical Response (remission and improvement) at Weeks 16, 24, and 52.

- Dose escalation: (without dose escalation, with dose escalation)
- Previous infliximab experience (infliximab naïve, prior exposure to infliximab)

8.1.7 Interim Analysis

An interim analysis of the primary endpoint and secondary efficacy variables as well as safety data collected from Baseline through Week 24 will be performed after the last subject in FAS population completes the 24-week period of the study. A database lock will be performed and any discrepant data will be clarified before the lock.

8.1.8 Pharmacokinetic Analyses

Pharmacokinetic

Adalimumab trough serum concentrations will be reported at each time point using descriptive statistics. The relationship between adalimumab concentrations and Clinical Response will be determined as appropriate.

Immunogenicity

AAA will be evaluated for each subject and rates of AAA positive will be calculated. As appropriate, the effect of AAA on adalimumab pharmacokinetics, efficacy variable(s), and treatment-emergent adverse events may be evaluated.

8.2 Determination of Sample Size

GPP is designated as the specified rare and intractable disease in Japan and patient number is quite limited. Assuming the clinical response rate of adalimumab in GPP is similar to that in plaque psoriasis, 50% to 60% as expected response rate in adalimumab treatment and 10% as a threshold response rate is hypothesized.

A sample size of 6 to 10 provides over 90% power to detect the difference between expected Clinical Response rate (50 to 60%) and threshold response rate (with no medication, 10%) in GPP, using a one sample Chi-square test with 2.5% one-sided significance level. Using Fisher's exact test, an exact binomial test with a nominal 0.025 one-sided significance level will have 82% power to detect the difference between the threshold proportion of 10% and the expected proportion of 50%.

Therefore, the target number of subjects is set 10 subjects, taking the study feasibility into consideration.

Threshold Response Rate	Expected Response Rate	Actual Power	No of Subjects
10%	50%	91.2%	10
10%	55%	91.6%	8
10%	60%	90.3%	6

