- Proportion of subjects taking topical co-medication for GPP (corticosteroid, vitamin D3, tacrolimus).

Determination of the Sample Size:

GPP is designated as the specified rare and intractable disease in Japan and patient number is quite limited. Assuming the Clinical Response rate of adalimumab in GPP is similar to PASI 75 response in plaque psoriasis, 50% to 60% as expected response rate in adalimumab treatment and 10% as a threshold response rate is hypothesized.

A sample size of 6 to 10 provides over 90% power to detect the difference between expected Clinical Response rate (50% to 60%) and threshold response rate (with no medication, 10%) in GPP, using a one sample Chi-square test with 2.5% one-sided significance level. Using Fisher's exact test, an exact binomial test with a nominal 0.025 one-sided significance level will have 82% power to detect the difference between the threshold proportion of 10% and the expected proportion of 50%.

Therefore, the target number of subjects is set 10 subjects, taking the study feasibility into consideration.

Statistical Methods (Continued):**Determination of the Sample Size (Continued):**

Threshold Response Rate	Expected Response Rate	Actual Power	No of Subjects
10%	50%	91.2%	10
10%	55%	91.6%	8
10%	60%	90.3%	6

Pharmacokinetic:

Adalimumab trough serum concentrations will be reported at each time point using descriptive statistics. The relationship between adalimumab concentrations and Clinical Response improvement will be determined as appropriate.

Immunogenicity:

AAA will be evaluated for each subject and rates of AAA positive will be calculated. As appropriate, the effect of AAA on adalimumab pharmacokinetics, efficacy variable(s), and treatment emergent adverse events may be evaluated.

Safety:

Adverse events (AEs), laboratory data and vital signs are the safety parameters in this study. Treatment-emergent AEs are defined as events that begin or worsen either on or after the first dose day of the study medication and within 70 days after the last dose of the study medication.

Treatment-emergent AEs will be summarized separately for the first half period (Week 0 to Week 24), the second half period (Week 24 to Week 52), and entire period (Week 0 to Week 52).

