6.0 Analysis Conventions

Unless otherwise specified, the efficacy and safety continuous variables will be summarized using the descriptive statistics (including mean, standard deviation, median, minimum and maximum), and for qualitative variables, the number (n) and percentage (%) of subjects with non-missing data per category will be the default summary presentation.

All statistical analyses will be conducted at a two-sided significance level of 0.050 or a one-sided significance level of 0.025 (when rounded to 3 decimal places).

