10.0 Efficacy Analysis**10.1 General Considerations**

This study is an open-label study without any comparator. The significant level is not defined, and descriptive statistics will be provided. These include the number of

observations, mean, standard deviation, minimum, median, and maximum for continuous variables; and number and percent for discrete variables. The exact 95% confidence intervals will be provided for the proportions. The analysis will be performed using SAS® (SAS Institute Inc., Cary, NC, USA). All efficacy analyses will be performed on the FAS.

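### The over-90% power claim for 6 to 10 subjects is a normal approximation; no test that holds one-sided 2.5% reaches 90% in any tabulated row

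*Protocol*

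**What the plan says.** Protocol 8.2 sets the assumptions as "50% to 60% as expected response rate in adalimumab treatment and 10% as a threshold response rate is hypothesized". It then says "A sample size of 6 to 10 provides over 90% power to detect the difference between expected Clinical Response rate" and the threshold rate, "using a one sample Chi-square test with 2.5% one-sided significance level". A table headed *Actual Power* gives:

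- 91.2% for 10 subjects (10% vs 50%)
- 91.6% for 8 subjects (10% vs 55%)
- 90.3% for 6 subjects (10% vs 60%)

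The next sentence, which refers to Fisher's exact test, says "an exact binomial test with a nominal 0.025 one-sided significance level will have 82% power" for 10% against 50%. It does not state the sample size. The target is then set at 10, with feasibility taken into account. The synopsis carries the same text and table; SAP 4.3 carries the text without the table.

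On whether any test will be done, SAP 6.0 says "All statistical analyses will be conducted at a two-sided significance level of 0.050 or a one-sided significance level of 0.025". SAP 10.1 says of efficacy "The significant level is not defined, and descriptive statistics will be provided", and adds "The exact 95% confidence intervals will be provided for the proportions". SAP 10.2, the primary analysis, makes no comparison with 10%.

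**The concern.** With 6 to 10 subjects and a 10% null rate, the expected number of responders under the null is 0.6 to 1.0. A normal approximation is unreliable there, both for the error rate and for the power. The plan nevertheless presents its results under a heading that suggests they are attained values.

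For the planning case of 10% against 50%, the reader meets two figures, 91.2% in the table and 82% in the text, and the less favourable one lacks the label *Actual*. The other two rows have no exact figure at all. At stake is whether the stated power is a property the design has at the stated error rate. A second, lesser question is whether the 10% threshold is for inference or only for planning.

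**Working it through.** **Inputs.** From Protocol 8.2: p0 = 0.10; (n, p1) = (10, 0.50), (8, 0.55), (6, 0.60); one-sided level 0.025.

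**Step 1: reproduce the plan's figures.** The uncorrected one-sample chi-square approximation is

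power = Φ( [√n (p1 − p0) − 1.96 √(p0(1 − p0))] / √(p1(1 − p1)) ), with 1.96 × √(0.10 × 0.90) = 0.588.

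- n=10: (1.2649 − 0.588)/0.5000 = 1.354; Φ = 0.912
- n=8: (1.2728 − 0.588)/0.4975 = 1.377; Φ = 0.916
- n=6: (1.2247 − 0.588)/0.4899 = 1.300; Φ = 0.903

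All three match the table. Using the Wald variance, a continuity correction or the arcsine transformation does not reproduce it.

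**Step 2: exact power with size held at or below 2.5%.** Take the smallest r with P(X ≥ r | n, 0.10) ≤ 0.025, then compute P(X ≥ r | n, p1).

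| n | p1 | Reject at | True size | Exact power | Stated |
|---|---|---|---|---|---|
| 10 | 50% | ≥4 | 0.0128 | 0.8281 | 91.2% |
| 8 | 55% | ≥4 | 0.0050 | 0.7396 | 91.6% |
| 6 | 60% | ≥3 | 0.0159 | 0.8208 | 90.3% |

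The first row can be checked by hand: 1 − (1 + 10 + 45 + 120)/1024 = 0.8281. It agrees with the disclosed 82%, so that sentence refers to n=10.

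**Step 3: could another test that holds 2.5% reach 90%?** The most powerful test of size exactly 0.025 also rejects with probability γ at the next lower count, where γ = (0.025 − size)/P(X = r − 1 | 0.10).

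- n=10: γ = 0.213; power 0.828 + 0.213 × 0.117 = 0.853
- n=8: γ = 0.604; power 0.740 + 0.604 × 0.172 = 0.843
- n=6: γ = 0.093; power 0.821 + 0.093 × 0.138 = 0.834

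These are upper bounds. No test at the stated level reaches 90% in any row.

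**Step 4: what the chi-square rule itself does.** It rejects when z > 1.96. The smallest rejecting count is 3 in every row (z = 2.11, 2.59 and 3.27).

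| n | True size of ≥3 | True power of ≥3 |
|---|---|---|
| 10 | 7.0% | 94.5% |
| 8 | 3.8% | 91.2% |
| 6 | 1.6% | 82.1% |

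At n=10 and n=8 power above 90% is obtained by exceeding the stated error rate. At n=6 the rule holds its level, but its power is 82.1%, not 90.3%.

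**Step 5: link to the planned interval.** If the exact 95% interval in SAP 10.1 is Clopper-Pearson, its lower limit is 6.7% at 3/10 and 12.2% at 4/10. It excludes 10% only from 4 responders, which is the exact rule in step 2. At 3/10 the chi-square test would reject while the interval still contains 10%.

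**Step 6: the planned n=10 across the assumed rates.** P(X ≥ 4) is 82.8% at 50%, 89.8% at 55% and 94.5% at 60%.

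**The case against.** The best defence is that the plan names its method. The tabulated values are correct arithmetic for the approximation. *Actual Power* can also be read as the power at the rounded-up sample size against a 90% target, since one subject fewer gives 0.8895, 0.8871 and 0.8604 under the same formula. The exact figure for the planned case is already disclosed, and n is fixed only after it. Part of the shortfall is discreteness: at n=8 the exact test uses only 0.5% of its 2.5%. The n=8 and n=6 rows do not describe this trial, and the efficacy analysis is descriptive.

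Much of this stands. The formula was applied correctly, the 82% is disclosed, two rows are illustrative, and nothing in conduct depends on the point. It does not rescue the claim. Removing discreteness by randomisation still leaves 83.4% to 85.3%. The 90.3% is wrong even for the named test. The approximate figure for 10% versus 50% still stands beside the exact one with the more favourable label. The conflict between SAP 6.0 and 10.1 is a separate, secondary matter and is not needed for the conclusion.

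**Conclusion.** The concern holds. At one-sided 2.5% the design does not have over 90% power in any tabulated row. Stated against exact power is 91.2% vs 82.8%, 91.6% vs 74.0%, and 90.3% vs 82.1%: overstatements of 8.4, 17.6 and 8.2 percentage points. This rests only on the plan's own rates, sample sizes and error rate, with responders treated as binomial and size required to be at most 2.5%. The statement about the planned interval additionally assumes Clopper-Pearson.

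The consequence is limited. Ten subjects remain justified by 82.8% exact power at 50% and by the rarity of the disease. It should be fixed because an unattainable figure appears in both documents. The SAP also leaves open whether the powered comparison will be made.

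**What to change.** 1. In the protocol synopsis, Protocol 8.2 and SAP 4.3, delete the chi-square power sentence and the reference to Fisher's test, which is a misnomer for a one-sample exact binomial test. Replace them with: *With 10 subjects, a one-sided exact binomial test of 10% at 0.025 (4 or more of 10; actual size 1.3%) has 82.8% power if the true rate is 50%, 89.8% at 55% and 94.5% at 60%.*
2. In the two protocol tables, change the power values to 82.8%, 74.0% and 82.1%, and head the column *Exact power*. Note that the 8- and 6-subject rows are illustrative and that power is not monotone in n because the test is discrete.
3. Make SAP 6.0 and 10.1 agree. The sponsor chooses. If efficacy is purely descriptive, say the power figure is for planning only. If the 10% threshold is inferential, say it will be read from the lower limit of the planned exact 95% interval, and name the interval method.

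Keep n=10. The cost is wording and three table values, with a less favourable stated power. There are no extra subjects and no change to conduct or to the reported interval.

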9.0 Ethics

9.1 Independent Ethics Committee (IEC) or Institutional Review Board (IRB)

GCP requires that the clinical protocol, any protocol amendments, the Investigator's Brochure, the informed consent and all other forms of subject information related to the study (e.g., advertisements used to recruit subjects) and any other necessary documents be reviewed by an IEC/IRB. The IEC/IRB will review the ethical, scientific and medical appropriateness of the study before it is conducted. IEC/IRB approval of the protocol, informed consent and subject information and/or advertising, as relevant, will be obtained prior to the authorization of drug shipment to a study site.

Any amendments to the protocol will require IEC/IRB approval prior to implementation of any changes made to the study design. The investigator will be required to submit, maintain and archive study essential documents according to International Conference on Harmonization (ICH) GCP.

Any serious adverse events that meet the reporting criteria, as dictated by local regulations, will be reported to both responsible Ethics Committees and Regulatory Agencies, as required by local regulations. During the conduct of the study, the investigator should promptly provide written reports (e.g., ICH Expedited Reports, and any additional reports required by local regulations) to the IEC/IRB of any changes that affect the conduct of the study and/or increase the risk to subjects. Written documentation of the submission to the IEC/IRB should also be provided to AbbVie.

9.2 Ethical Conduct of the Study

The study will be conducted in accordance with the protocol, International Conference on Harmonization (ICH) guidelines, applicable regulations and guidelines governing clinical study conduct and the ethical principles that have their origin in the Declaration of Helsinki. Responsibilities of the clinical investigator are specified in [Appendix A](#).

9.3 Subject Information and Consent

The investigator or his/her representative will explain the nature of the study to the subject, and answer all questions regarding this study. Prior to any study-related screening procedures being performed on the subject, the informed consent statement, including the acceptability of photography of skin lesion, will be reviewed and signed and dated by the subject, and the person who administered the informed consent. If the subject is < 20 years old, a subject's parent or legal guardian must be explained and willing to give written informed consent. A copy of the informed consent form will be given to the subject and the original will be placed in the subject's medical record. An entry must also be made in the subject's dated source documents to confirm that informed consent was obtained prior to any study-related procedures and that the subject received a signed copy.

Information regarding incentives for subjects and information regarding provisions for treating and/or compensating subjects who are harmed as a consequence of participation in the study can be found in the informed consent form.

9.3.1 Informed Consent Form and Explanatory Material

The Principal Investigator will prepare the consent form and explanatory material required to obtain subject's consent to participate in the study with the cooperation of the sponsor and will revise these documents as required. The prepared or revised consent forms and explanatory material will be submitted to the sponsor. Approval of the IRB will be obtained prior to use in the study.

9.3.2**Revision of the Consent Form and Explanatory Material**

When important new information related to the subject's consent becomes available, the Principal Investigator will revise without delay the consent form and explanatory material based on the information and will obtain the approval of the IRB prior to use in the study. The Investigator will provide the information, without delay, to each subject already participating in the study, and will confirm the intention of each subject to continue in the study or not. The Investigator will also provide further explanation using the revised consent form and explanatory material and will obtain written consent from each subject of their own free will to continue participating in the study. If the subject is < 20 years old, a subject's parent or legal guardian must be explained and willing to give written informed consent.

10.0**Source Documents and Case Report Form Completion****10.1****Source Documents**

Source documents are defined as original documents, data and records. This may include hospital records, clinical and office charts, laboratory data/information, subjects' dosing diaries or evaluation checklists, pharmacy dispensing and other records, recorded data from automated instruments, microfiches, photographic negatives, microfilm or magnetic media, and/or x-rays. Data collected during this study must be recorded on the appropriate source documents.

The following assessments that will be completed by subjects on paper will be considered source documentation:

- DLQI
- SF-36 version 2.0

The following contents recorded in eDRF may also be used as source, and will require an Investigator approval on the eCRF as verification of the accuracy of the information:

- Route of drug administration
- Effect of the pre-treatment for GPP
- Reasons for pre-treatment and concomitant treatment for GPP
- Diagnostics, time course, severity, frequency and relationship to study drug, alternative etiology, medication for recovery, and seriousness for either SAEs or Nonserious AEs
- Investigator's comments
- Reason for Premature discontinuation for subject
- Reason why the physician or nurse performed injection of study drug, after self-injection started (if applicable)

The investigator(s)/institution(s) will permit study-related monitoring, audits, IEC/IRB review, and regulatory inspection(s), providing direct access to source data documents.

10.2 Case Report Forms

Case Report Forms (CRFs) must be completed for each subject screened/enrolled in this study. These forms will be used to transmit information collected during the study to AbbVie and regulatory authorities, as applicable. The CRF data for this study are being collected with an electronic data capture (EDC) system called Rave® provided by the technology vendor Medidata Solutions Incorporated, NY, USA. Data entry should be completed within 5 days after a subject visit or results are available. The EDC system and the study-specific eCRFs will comply with Title 21 CFR Part 11. The documentation related to the validation of the EDC system is available through the vendor, Medidata, while the validation of the study-specific eCRFs will be conducted by AbbVie and will be maintained in the Trial Master File at AbbVie.

The investigator will document subject data in his/her own subject files. These subject files will serve as source data for the study. eCRF data required by this protocol will be recorded by investigative site personnel in the EDC system, except for subject-completed questionnaires, which will be completed on paper by the subject then transcribed into the

EDC system by site personnel. All data entered into the eCRF will be supported by source documentation.

The investigator or an authorized member of the investigator's staff will make any necessary corrections to the eCRF. All change information, including the date and person performing the corrections, will be available via the audit trail, which is part of the EDC system. For any correction, a reason for the alteration will be provided. The eCRFs will be reviewed periodically for completeness, legibility, and acceptability by AbbVie personnel (or AbbVie's representatives). AbbVie (or AbbVie's representatives) will also be allowed access to all source documents pertinent to the study in order to verify eCRF entries. The principal investigator will review the eCRFs for completeness and accuracy and provide his or her electronic signature and date to eCRFs as evidence thereof.

Medidata will provide access to the EDC system for the duration of the trial through a password-protected method of internet access. Such access will be removed from investigator sites at the end of the site's participation in the study. Data from the EDC system will be archived on appropriate data media (CD-ROM, etc.) and provided to the investigator at that time as a durable record of the site's eCRF data. It will be possible for the investigator to make paper printouts from that media. The following assessments will be completed by subjects on paper:

- DLQI
- SF-36 version 2.0

Site staff will verify completion of these forms. All questionnaires must be legible and completed in indelible ballpoint ink. Any necessary corrections are to be made by drawing a single line through the incorrect entry and writing in the revision, the date of the correction, the reason for the correction, and the initials of the study subject who is making the correction. Data are not to be obliterated by blacking out, using correction fluid or by erasing the original entry.

The questionnaire administrator will review the questionnaire for completeness and accuracy. The subject-completed questionnaires will be transcribed into the EDC system by study personnel. The completed paper questionnaire will be considered source documentation.

